17 β -Estradiol will be administered to group A treatment arm intravaginally. The assigned dosage will be one vaginal tablet daily for two weeks then one vaginal tablet twice a week for 10 weeks. Participants will be carefully monitored for any changes in clinical condition in each follow-up visits using logbook. It is important to clarify that we are not using 17 β -Estradiol (Vagifem®) 25 mcg as the study drug. Although 17 β -Estradiol 25 mcg is frequently mentioned in literature reviews and has been historically used for treating vaginal dryness, this drug is currently not available in Thailand. Therefore, we are using 17 β -Estradiol (Femiest®) 10 mcg as an alternative for our study drug. Notably, 17 β -Estradiol 10 mcg has been shown to provide a therapeutic dose equivalent to that of 17 β -Estradiol 25 mcg for treatment, as stated by the FDA. This decision ensures that participants receive an effective and appropriate dosage while adhering to the availability of medications in our region.

- **Placebo**

Placebo will be administered to group B treatment arms intravaginally. The assigned dosage will be one vaginal tablet daily for two weeks then one vaginal tablet twice a week for 10 weeks. Participants will be carefully monitored for any changes in clinical condition in each follow-up visits. Placebo is produced by Chulalongkorn University Drug and Health Products Innovation & Promotion Center, Faculty of Pharmaceutical Sciences, Chulalongkorn University. Details for presentation and packing are as follows;

Appearance	White, round, biconvex with "E" imprint one side
Weight	106 - 110 mg
Hardness	4.1 - 4.8 kP

Thickness	3.26 - 3.3 mm
Diameter	6.02 - 6.03 mm
Disintegration time	4 min 58sec - 7min 42sec
pH	7.18
Placebo contains	
 1. Agglomerated Lactose 2. Microcrystalline cellulose PH 102 3. Magnesium stearate

Both subject groups will be counseled on potential signs/symptoms of adverse events and post-marketing experience, such as breast pain, peripheral edema, and postmenopausal bleedings. Due to the vaginal administration and minimal systemic absorption, it is unlikely that any clinically relevant drug interactions will occur with 17 β -Estradiol. However, interactions with other locally applied vaginal treatments will be considered and advised to the patients. If a dose is forgotten, participants will be advised that it should be taken as soon as he/she remembers. A double dose should be avoided.

Random allocation

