
Each participant in the study will receive a prescription for the research drug, an adequate supply to cover a 12-week treatment duration. This drug will be uniformly packaged within identical containers, featuring a unique alphanumeric code and detailed usage instructions on the label, thereby avoiding the inclusion of the original medication name. The data analysis will be performed by a statistician who will be the sole individual privy to the allocation of drug A or drug B to their respective groups. It is essential to note that the statistician will remain unaware of which of the two is the active drug and which is the placebo. Additionally, an independent statistician will maintain a sealed randomization list as a contingency. Allocation will be as follows;

Group A

17 β -Estradiol 10 mcg (Femiest® Haupt Pharma Munster GMBH, Muenster, Germany
(ESTRADIOL HEMIHYDRATE 0.0103 milligram)

Group B

Placebo

III. Third Visit

At four weeks after 2nd visit, the following study procedure will be performed;

- Bladder diary, the participant will be reminded to provide a three-day diary prior to schedule visit date.
- ICIQ-FLUTS
- ICIQ-LUTSqol
- PGI-I
- Vaginal pH
- Urethral maturation index (UMI)

Participants will also have clinical evaluation and vital signs measurements evaluated.

Compensation for participants will be provided.

IV. Fourth and Final Visit

At eight weeks after 3rd visit, the following study procedure will be performed;

- Pelvic exam
- Pelvic floor muscle strength measured as Brink scale
- Bladder diary, the participant will be reminded to provide a three-day diary prior to schedule visit date.
- ICIQ-FLUTS
- ICIQ-LUTSqol
- PGI-I
- Vaginal pH
- Urethral maturation index (UMI)

Participants will also have clinical evaluation and vital signs measurements evaluated.

Compensation for participants will be provided. Overall study procedures and flow diagram for study are outlined in topic No.8 Protocol flow chart.

7.5) Sample Preparation, Processing, Handling, Storage

- **Vaginal pH**

To assess pH, a piece of litmus paper (MQuant® pH-indicator stripe) will be placed on the lateral vaginal wall until moistened. A pH of 4.6 or greater indicates vulvovaginal atrophy

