The procedure commonly incorporates the utilization of Cybow™ 10-urinalysis test strip, which are advanced diagnostic tools designed to analyze multiple urine parameters simultaneously. Initially, a fresh clean-voided midstream urine sample is collected and visually inspected for its

color, clarity, and odor. Subsequently, the Cybow strip is immersed into the urine specimen for a specific duration, enabling the strip's chemical pads to react with the components in the urine. These pads, strategically embedded with reagents, undergo color changes in response to the presence and concentration of specific analytes, including but not limited to pH, protein, glucose, ketones, nitrites, leukocytes, bilirubin, and urobilinogen. The strip is then carefully removed and placed on a flat surface, allowing for accurate color comparison with standardized color charts to quantify the concentration of each parameter. For this research purpose, exclusion of urinary tract infection is imperative for eligible criteria.

Interpretation: In the event of leukocytes displaying a concentration of one plus (1+) or higher, or a positive nitrite result, these findings could be indicative of a urinary tract infection (UTI). It is imperative to note that the presence of a UTI serves as an exclusion criterion during the evaluation process.⁽³⁹⁾

7.6) Statistical analysis

Demographics for enrolled participants will be tabulated and described for each study group including age, ethnicity, occupation etc. All clinical and laboratory data related to objectives will be summarized and compared for each group. Appropriate statistics will be calculated to summarize and compare the range, means, medians, etc., and variability of numerical data. Confidence limits (95%) for means, geometric means and proportions will be calculated. Graphical summaries (e.g., box plots, histograms) will be used to describe and compare distributions of numeric variables. Frequency tables will be used to summarize distributions for discrete data. All clinical and laboratory data related to outcomes will be summarized and compared in the two regimens. T-tests and chi-square tests will be used to assess the statistical significance of differences in two means (possibly log-transformed) or proportions. Descriptive summaries of serious adverse events, subject discontinuations due to adverse events, and potentially clinically significant abnormal values (clinical laboratory or vital signs) will also be provided.

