6. Willing to adhere to the research protocol and actively participate in the scheduled follow-up

appointments as delineated within the framework of this study

- **Exclusion criteria**

1. Contraindication for estrogen therapy: undiagnosed abnormal vaginal bleeding, previous thromboembolic event, breast cancer, gynecologic/genitourinary malignancy, active liver disease
2. Pelvic organ prolapse of anterior compartment stage III and IV
3. Immunocompromised patient or taking immunosuppressant drug
4. History of antibiotics drug use within the past 7 days
5. History of bladder outlet obstruction
6. History of using anti-muscarinics, β 3-adrenoceptor agonists, vaginal energy-based devices (laser and radiofrequency) or electromagnetic energy-based therapies within the past 2 weeks
7. History of documented positive urine culture in the past 6 weeks
8. Have an allergic reaction to study's drug
9. Any other significant finding that in the opinion of the investigator would increase the risk of having an adverse outcome from participating in this study

10. Duration of data collection

It will take about 12 months for data collection, analyses and manuscript writing. All steps will start after the IRB ethical approval. If the research continues beyond the specified time or Ethics committee License expired, the investigators will request for renewal every year.

11. Risk of the study

There will be no physical, psychological or legal risks related to this study. Estradiol 10 mcg has a low dose and is safe. The adverse events observed with a higher frequency in patients treated with Estradiol 10 micrograms as compared to placebo and which are possibly related to treatment are presented as follows.⁽⁴⁰⁾

stem organ class	Common $\geq 1/100$ to $< 1/10$	Uncommon $\geq 1/1,000$ to $< 1/100$	Rare $\geq 1/10,000$ to $< 1/1,000$
Infections and infestation		Vulvovaginal mycotic infection	
Nervous system disorders	Headache		
Gastrointestinal disorders	Abdominal pain	Nausea	
Reproductive system and breast disorders	Vaginal haemorrhage, vaginal discharge or vaginal discomfort		
Skin and subcutaneous tissue disorders		Rash	
Investigations		Weight increased	
Vascular disorders		Hot flush Hypertension	

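### Does section 7.6 need to name a by-arm table of non-serious adverse events?

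*Combined protocol and SAP*

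**What the plan says.** The safety content of section 7.6 is one sentence, which promises "Descriptive summaries of serious adverse events, subject discontinuations due to adverse events, and potentially clinically significant abnormal values", the last of these covering laboratory results and vital signs. It does not say that these summaries are by arm. Two other sentences in 7.6 do promise a comparison between groups. One covers data tied to the objectives. The other reads "All clinical and laboratory data related to outcomes will be summarized and compared in the two regimens". Sections 6 and 7.3 list storage symptoms, quality of life, global improvement, urethral maturation and vaginal pH, and no safety objective or outcome. Section 7.6 also provides, without restriction to any kind of variable, for frequency tables of discrete data and 95% confidence limits for proportions.

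Section 11 introduces a table of "The adverse events observed with a higher frequency in patients treated with Estradiol 10 micrograms as compared to placebo". Its common column (1 in 100 to below 1 in 10) holds headache, abdominal pain and "Vaginal haemorrhage, vaginal discharge or vaginal discomfort". The same section opens with "There will be no physical, psychological or legal risks related to this study".

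On collection, the trial-treatment part of section 7.4 says "Both subject groups will be counseled on potential signs/symptoms of adverse events". Women on estradiol are to be "monitored for any changes in clinical condition in each follow-up visits using logbook". The placebo paragraph has the same monitoring sentence without the logbook. For both the third and the fourth visit the plan adds "Participants will also have clinical evaluation and vital signs measurements evaluated".

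**The concern.** Read literally, a woman on estradiol who has headache or vaginal discharge, stays on treatment and has no abnormal value falls outside all three named safety summaries. She also falls outside the two by-arm sentences, because no objective or outcome concerns safety. A report could then satisfy 7.6 and never show, side by side, the events that section 11 itself expects more often on the active drug.

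Two wording points add to the impression. The logbook is mentioned for one arm only, which would suggest unequal ascertainment if taken at face value. The denial of physical risk stands directly above a table of adverse events. At stake is whether readers see complete and comparable harms data. The efficacy result is not at stake.

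**Working it through.** **Denominator.** Section 9 gives p1 = 0.63, p2 = 0.32, alpha 0.05 and beta 0.2; allocation is 1:1. The mean proportion is (0.63 + 0.32)/2 = 0.475. The plan's formula gives

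n = [1.96 × √(2 × 0.475 × 0.525) + 0.8416 × √(0.63 × 0.37 + 0.32 × 0.68)]² / 0.31² = 39.5,

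that is 40 against the stated 39. The stated 43 is 39 × 1.1 = 42.9 rounded up, and 2 × 43 = 86. The plan's figures reproduce within one woman per arm. I use 43 per arm, since a woman who has an event and then leaves still belongs in a safety count. Figures for 39 are given for comparison.

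**Would such events occur?** Section 11's common band is 1% to below 10%.

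| Women on estradiol | Expected with a given event | Chance of at least one |
|---|---|---|
| 43 | 43 × 0.01 = 0.43 to just under 43 × 0.10 = 4.3 | 1 − 0.99^43 = 35% to just under 1 − 0.90^43 = 99% |
| 39 | 0.39 to just under 3.9 | 32% to just under 98% |

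So some of the common events may well appear. For the six uncommon events (0.1% to below 1%), the expected number is 43 × 0.001 = 0.04 to just under 43 × 0.01 = 0.43 women each.

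**What would a by-arm table show?**
- An assumed split of 4/43 v 1/43 is 9.3% v 2.3%, a difference of 7.0 points, Newcombe 95% CI -4.3 to 19.4. With 39 per arm it is 7.7 points (-4.6 to 21.2).
- For 0 of 43, the exact two-sided 95% upper limit is 1 − 0.025^(1/43) = 8.2%; for 0 of 39 it is 9.0%. Most of the common band would remain possible.
- A 0 v 0 row with 43 per arm gives about -8.2 to +8.2 points.
- Power to separate 10% from 1% with 43 per arm is 45%; to separate 5% from 1% it is 19%.

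The table would be descriptive only.

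**Which events does the text leave unnamed?**
- Hypertension is reached through abnormal vital signs.
- Any event that ends treatment is reached through discontinuations, and any serious event through the serious-event summary.
- What remains is non-serious symptoms in women who continue. These are discrete data, so the general sentences on frequency tables and limits for proportions can take them, although those sentences name neither adverse events nor arms.

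**Could the logbook be used in one arm only?** Section 7.4 describes identical coded containers, and the trial is double-blind. Site staff could not give a logbook to estradiol users alone, so the mismatch is a drafting slip with no effect on ascertainment.

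**The case for a change.** The strongest case for a change is that the general sentences in 7.6 do not name adverse events, that even the three named safety summaries are not said to be by arm, and that comparison with placebo matters here. The background section describes nocebo adverse events in trials of overactive bladder, so counts on estradiol mean little without the placebo column. Section 13 also argues that the drug has fewer side effects than alternatives, and a trial that leans on tolerability should report it. The remedy would be cheap: one descriptive table.

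The reading of the text is correct, and by-arm reporting is plainly the right practice. It does not follow that the plan is defective. Nothing in 7.6 tells the analyst to leave non-serious events out or to pool the arms. The change would write down a table that is ordinarily produced anyway and would replace no wrong method.

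A request for a standard adverse-event question at visits 3 and 4 is weaker still. Section 7.4 refers to the section 8 flow chart for the overall procedures, and that chart cannot be seen in the text available, so its content cannot be called absent. Difference intervals for 11 listed events, six of them uncommon, would be a matter of preference, because most of those rows would hold zeros or ones.

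**Conclusion.** No change to the plan is needed. The gap is real but narrow: section 7.6 does not spell out a table of all adverse events by arm. Analysts would fill it sensibly from events that the plan already has ways of noticing in both arms. With 0.43 to just under 4.3 of 43 women expected per common event, such a table carries descriptive information and cannot support a conclusion for or against a safety difference. The primary outcome, the sample size of 86, randomisation and blinding are all untouched.

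This rests on three assumptions: section 11's frequency bands apply roughly to this population; events noted at visits 3 and 4 or in the logbook are recorded alike in both arms; and the recorded events are tabulated by randomised arm, as is usual. The logbook wording in the two treatment paragraphs, and the risk sentence above the table in section 11, are inconsistent and should be reconciled when the text is next edited. They are clerical points and alter no result.

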Estrogen has the potential to provide therapeutic advantages in managing irritative voiding symptoms, such as urgency, frequency, and urge urinary incontinence. The precise mechanism by which the medication induces the reversal of urogenital atrophy or its direct impact on the lower urinary tract remains uncertain. One challenge in comprehending the contradictory data now available on the subject pertains to the utilization of multiple estrogen formulations, varying dosages, diverse methods of administration, and the inconsistent use of concomitant progesterone. There exists substantial evidence supporting the efficacy of low-dose vaginal estrogen treatment in reversing urogenital atrophy, encompassing both the symptoms and cytological changes.^(20, 21)

Review literatures

- **Comparison: Vaginal estradiol 25 mcg versus placebo**

Research title	country	year	Dosage	F/U	Outcome Measurement	Results
Low-dose 17beta-estradiol vaginal tablets in the treatment of atrophic vaginitis: a double-blind placebo-controlled study ⁽¹⁴⁾	Denmark	Eriksen PS 1991	estradiol 25 mcg vs placebo	12 weeks	urological symptoms change	Vg E -> improve 62.8% placebo -> improve 32.4%
Local estrogen treatment in patients with urogenital symptoms ⁽²²⁾	Croatia	Simunic 2003	estradiol 25 mcg vs placebo	12 months	symptoms/signs of urinary atrophy Dysuria Frequency/nocturia Urinary tract infection Urinary incontinence Urinary atrophy	n=330->84 n=371->74 (Improve 80%) n=186->49 n=245->106 n=406->121
Vaginal estradiol for the treatment of lower urinary tract symptoms in postmenopausal women--a double-blind placebo-controlled study ⁽²³⁾	England	Cardozo 2001	estradiol 25 mcg vs placebo	12 weeks	N/A	A significantly greater reduction in the symptom of urinary urgency on visual analogue score was detected for women in stratum A (sensory urgency)

- **Weber MA et al. (2015)**

Local Estrogen for Pelvic Floor Disorders: A Systematic Review

Comparison: Vaginal estrogen versus placebo or no treatment

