To date, no prior investigations have been conducted employing robust methodological approaches to assess the efficacy of 17 β -Estradiol at a dosage of 10 mcg in the treatment of Lower Urinary Tract Symptoms (LUTS) in postmenopausal women, particularly in comparison to a placebo control group. This notable gap in the existing literature underscores the need for a comprehensive and rigorously designed study to investigate the potential therapeutic benefits of 17 β -Estradiol in alleviating LUTS among postmenopausal women, while concurrently establishing its superiority or non-inferiority relative to a placebo intervention. Such an investigation would not only contribute significantly to our understanding of this therapeutic avenue but also provide valuable insights into the management of storage symptoms of LUTS in this specific population.

6. Objective

Primary objective

To determine the efficacy of vaginal 17 β -estradiol treatment in alleviating storage symptoms of LUTS in comparison to placebo.

Secondary objective

- To determine the efficacy of vaginal 17 β -estradiol treatment on urethral maturation index and vaginal pH in comparison to placebo.
- To assess the impact of vaginal 17 β -estradiol treatment on the overall quality of life and the patient's global improvement (PGI) perception.

7. Study Objectives and Study Design Overview

7.1) Study design

The clinical study is a two arm, randomized, double-blind, placebo-controlled trial study of postmenopausal women who suffer from storage symptom of LUTS.

7.2) Population

Postmenopausal women who suffer from storage symptom of LUTS.

7.3) Outcomes

Primary outcome

Storage symptom improvement: will be evaluated using “the International Consultation on Incontinence Questionnaire-Female Lower Urinary Tract Symptoms: ICIQ-FLUTS” (Validated Questionnaire in Thai version)⁽²⁸⁾

It comprises of 5 items, each represent the storage symptoms in the following items;

- Item 2a) nocturia
- Item 3a) urgency
- Item 5a) daytime frequency
- Item 9a) UUI
- Item 11a) SUI

Each item will have 2 parts of sub-categories questions are severity and bothersome.

- In severity categories: the questionnaire has established ranging from 0, denoting the absence of any severity, to 4, indicating the highest level of symptom severity. The cumulative point range across all questionnaire items spans from 0 to 20.

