7.7) Study Subjects

Collect data and publicizing invitations to participate in research “Efficacy of Vaginal 17 β -Estradiol on the Urinary Storage Symptoms in Postmenopausal Women: A Randomized Double-blind, Placebo-controlled Study” in Outpatient departments, Department of Obstetrics & Gynecology, Faculty of Medicine Ramathibodi Hospital

[figure not shown]
7.8) Research site

Outpatient departments, Department of Obstetrics & Gynecology, Faculty of Medicine
Ramathibodi Hospital

7.9) Research plan

Activities	2023					2024												2025		
	8	9	10	11	12	1	2	3	4	5	6	7	8	9	10	11	12	1	2	3
1. Literature review and proposal preparation	■	■	■																	
2. Proposal submission and approval			■	■	■															
3. Data collection and analysis								■	■	■	■	■	■							
4. Manuscript writing and submission																■	■	■	■	

8. Protocol Flow Chart

9. Sample size calculation and inclusion/exclusion criteria

- **Sample size calculation**

The sample size is calculated using two independent population proportions formula.

$$n_1 = \left[\frac{z_{1-\frac{\alpha}{2}} \sqrt{\bar{p}\bar{q} \left(1 + \frac{1}{r}\right)} + z_{1-\beta} \sqrt{p_1 q_1 + \frac{p_2 q_2}{r}}}{\Delta} \right]^2$$

$$\Delta = p_1 - p_2, \quad \bar{p} = \frac{p_1 + p_2 r}{1 + r}, \quad r = \frac{n_2}{n_1}$$

$$q_1 = 1 - p_1, \quad q_2 = 1 - p_2, \quad \bar{q} = 1 - \bar{p}$$

Proportion in group1 (p1) = 0.63

Proportion in group2 (p2) = 0.32

alpha(α) = 0.05 , Beta(β) = 0.2

According to Eriksen PS, Rasmussen H (1991)⁽¹⁴⁾ , after 12 weeks, 62.8% of the women with urological symptoms underwent a change for the better in the estradiol (Vagifem®) group compared to 32.4% in the placebo group. (P < 0.001). With sample size (n) equal to 39 subjects per group and add drop out at rate of 10%, which is equal to 43 subjects per group. The total number of sample size will be 86 subjects.

- **Inclusion criteria**

1. Presenting with storage phase symptom score more than/equal to 1 evaluated by the ICIQ-FLUTS questionnaire in these items

- Item 2a) nocturia and/or
- Item 3a) urgency and/or
- Item 5a) daytime frequency and/or
- Item 9a) UUI and/or
- Item 11a) SUI

2. Being natural or surgical menopause for more than 1 year

3. Absence of urinary tract infection or other identifiable cause

4. Not using hormone replacement therapy or any route of estrogen within 4 weeks

5. Never undergone onabotulinumtoxinA therapy, PTNS, or neuromodulation for OAB treatment

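### The primary outcome reduces a 0–20 storage score to any fall versus no fall; a baseline-adjusted comparison of the score should have more power with the same women

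*Combined protocol and SAP*

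**What the plan says.** Section 7.3 (Outcomes) builds the primary outcome from five ICIQ-FLUTS storage items, each scored 0 to 4 for severity: "The cumulative point range across all questionnaire items spans from 0 to 20". A parallel bother total runs from 0 to 50. The same section then sorts the result into two classes. A post-treatment score below the pre-treatment score is improved, and an equal or higher score is not improved.

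Section 7.4 collects the questionnaire at visit 2 (baseline), at visit 3 four weeks later, and at visit 4 eight weeks after that, which is 12 weeks from baseline.

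Section 7.6 (Statistical analysis) lists t-tests for means and chi-square tests for proportions. It ties neither to the primary outcome and names no baseline-adjusted model.

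Section 9 uses a two-proportion formula with "Proportion in group1 (p1) = 0.63", 0.32 for placebo, alpha 0.05 and beta 0.2. The result is "sample size (n) equal to 39 subjects per group", raised to 43 for 10% dropout. The rates come from a 12-week placebo-controlled study, in which "62.8% of the women with urological symptoms underwent a change for the better in the estradiol (Vagifem®) group compared to 32.4" per cent on placebo, and which the literature table lists under "Comparison: Vaginal estradiol 25 mcg versus placebo". In Section 7.4, the Trial Treatment text explains that 10 mcg is used because, of the 25 mcg tablet, "this drug is currently not available in Thailand". It calls the lower dose therapeutically equivalent to "25 mcg for treatment, as stated by the FDA".

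**The concern.** Cutting a 21-level score at any fall versus no fall throws away the size of each woman's change and gives the baseline score no role as a covariate. With 39 analysed women per arm and a target of 80%, there is little power to give away. If the score holds usable information, a real benefit could be missed that the data already being collected would have shown.

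Two readings are needed. Section 7.3 speaks of a mean score, which is taken here as a rule applied to each woman because Section 9 plans on proportions of women. Section 7.3 also does not say whether the severity or the bother total drives the classification. Severity is assumed.

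**Working it through.** **1. Reproduce the plan's figure.** The formula printed in Section 9 with equal arms is n = {[1.960·√(2p̄q̄) + 0.8416·√(p₁q₁ + p₂q₂)] / (p₁ − p₂)}².

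- Rounded inputs 0.63 and 0.32: p̄ = 0.475, and the two roots are 0.7062 and 0.6713. n = [(1.3842 + 0.5650)/0.31]² = 39.5. The plan states 39.
- Cited rates 0.628 and 0.324: p̄ = 0.476, and the roots are 0.7063 and 0.6728. n = [(1.3843 + 0.5662)/0.304]² = 41.2, so 42.
- Dropout: 39 × 1.1 = 42.9, so 43, as stated.

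Three roundings go the same way: 62.8% up to 0.63, 32.4% down to 0.32, and 39.5 down to 39.

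**2. Power of the responder test.** The same formula solved for power is Φ{[(p₁ − p₂)√n − 1.960·√(2p̄q̄)] / √(p₁q₁ + p₂q₂)}.

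- Rounded rates, n = 39: Φ[(1.9359 − 1.3842)/0.6713] = 79.4% (exact chi-square 80.5%).
- Cited rates, n = 39: Φ[(1.8985 − 1.3843)/0.6728] = 77.8% (exact 78.9%).
- Cited rates, all 43 evaluable: 81.7% (exact 81.1%).

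**3. What the score comparison can detect.** A two-sample t-test with 39 per arm has 80% power for 0.643 SD of change. For an assumed SD of 2, 3 or 4 points that is 1.3, 1.9 or 2.6 points. If variances are equal at the two visits and the baseline–follow-up correlation is ρ, ANCOVA multiplies the SD of change by √((1 + ρ)/2). At an assumed ρ of 0.5 the factor is 0.866, so the detectable difference is 0.643 × 0.866 = 0.56 SD.

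**4. Score power matched to the two cited improvement rates.** The shape of the change distribution is assumed. For a normal change, d = Φ⁻¹(0.628) − Φ⁻¹(0.324) = 0.327 + 0.457 = 0.783, and the t-test has 92.7% power. The simulations use integer scores with a floor at 0.

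| Assumed change, 39 per arm | Chi-square | ANCOVA on score |
|---|---|---|
| Normal, baseline mean 7, SD 3 | 79–80% | 92% |
| Normal, baseline mean 2–3 | 79% | 89–90% |
| Logistic | 79% | 84% |
| Laplace (heavy tails) | 79% | 61–62% |
| Mixture: improvers gain 3 points (SD 0, 1.5 or 2.5), others unchanged | 79% | 76.5%, 62.5%, 54.5% |

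With no treatment effect, rejection rates were 5.0–5.6% for chi-square and 4.7–5.2% for ANCOVA, so the change does not inflate false positives.

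**5. Does the gain need placebo women to get worse?** The normal calibration does imply this: if only 32.4% of placebo women fall, the mean placebo change is +0.457 SD. Two checks remove that feature.

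- Hold d at 0.783 and let the placebo any-fall rate be 50% (mean change zero), 60% or 70% (placebo improves). Responder power at 39 per arm becomes about 75%, 70% or 62%. The t-test stays at about 93%. At 50%, for example, the active rate is Φ(0.783) = 0.783, and the formula gives Φ[(0.283·√39 − 1.329)/0.648] = 75%.
- A simulation built the total from five 0–4 items with measurement noise, with placebo mean change zero or improving and the effect present in all women or in only 30–50% of them. ANCOVA was ahead of chi-square in all 36 settings.

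**The case against.** The strongest reply is that the attractive figures in step 4 come from models in which placebo women worsen on average. The protocol's own section on placebo and nocebo reports improvement on placebo, and both arms receive a behaviour guidebook. This stands against using 93% as a forecast. It does not remove the gain, because step 5 keeps it with placebo stable or improving.

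A second reply is that some models reverse the ranking. The Laplace and mixture rows do. So do integer-change models that match 62.8% and 32.4% with an equal share worsening in each arm: the t-test then has 62–79% power with nobody worsening, 45–54% with 10% and 34–41% with 20%. This stands as a real limit. These cases need very heavy tails, or non-responders whose score does not move at all, or a treatment that moves women from no change to improvement without altering the share who worsen. A noisy five-item questionnaire makes exact stability unlikely, but the documents cannot exclude it. It also follows that the shape of the change distribution, and not the SD alone, decides the gain.

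Third, Section 7.6 already permits t-tests on scores, and any improvement mirrors the source study's outcome. Both are true. Neither makes the score analysis primary or adjusts it for baseline.

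A reader might also infer that planning a 10 mcg trial on 25 mcg rates is an error that calls for a discount or a power reserve. The documents do not support that. Section 7.4 asserts equivalence, and the literature review describes 10 mcg relief of urinary and genital symptoms, though mainly in atrophy. The Knowledge gap text says "no prior investigations have been conducted employing robust methodological approaches to assess the efficacy of" 10 mcg in LUTS, so the question is open, but an open question is not a mistake. Any retained fraction of the effect would be invented.

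**Conclusion.** The point holds as a matter of efficiency. The randomised comparison and its responder test are valid, but the chosen primary outcome uses less of the collected data than it could. With ordinary measurement noise, ANCOVA on the 12-week severity score has more power than chi-square at 39 per arm. The direction rests on that noise assumption. The size cannot be fixed from the documents, which give no SD, correlation or shape of change, so no single figure such as 93% should be quoted as the expected power.

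The responder power at the cited rates is 77.8% (exact 78.9%), a small shortfall due to rounding. A reader might infer that the trial is seriously underpowered. It is not on the plan's own assumptions, and with all 43 per arm evaluable power is 81–82%.

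**What to change.** Before unblinding:

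1. Make the primary analysis the between-arm difference in the 12-week ICIQ-FLUTS storage severity score (0–20), by ANCOVA adjusted for the visit 2 score. Keep improved/not improved as a secondary outcome.
2. Restate power on the score with a stated SD: 80% power at 39 per arm for about 0.64 SD unadjusted. The blinded pooled distribution of 12-week change can show whether tails are very heavy or many women do not change.
3. If the responder outcome stays primary, restate power at 39 per arm as about 78% (exact 79%) at 62.8% versus 32.4%.

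This needs no extra women, visits or measurements. The costs are a protocol amendment, a treatment effect that is less intuitive than a percentage improved (the secondary outcome covers this), and the chance of lower power if changes turn out heavy-tailed or all-or-nothing.
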